## 7.4.2 Secondary analysis

The Kaplan-Meier (KM) estimates of failure rate per treatment group will be presented graphically. In addition, certain quantiles of the failure times (e.g. 2.5%, 5%, 7.5% and 10% quantiles) will be provided per treatment group. Kaplan-Meier estimates for failure rates at 6 months, 1, 1.5, 2, etc years after randomisation will be presented per treatment group.

The two-sided p-value resulting from the log-rank test will be presented for completeness.

Descriptive statistics will display the number of patients at risk, the number of patients with event, the incidence (proportion of patients with event), the time at risk for event and the incidence rate (number of patients with event per 1000 years at risk) per treatment group.

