#### Primary endpoint

The primary endpoint is time to the first occurrence of any of the following adjudicated components of the composite endpoint (**43**-point MACE): CV death (~~including fatal stroke, fatal MI, and sudden death~~), non-fatal MI (~~excluding silent MI~~), **or** non-fatal stroke, ~~hospitalisation for unstable angina pectoris~~.

Patients without occurrence of a specific endpoint (composite endpoint or individual components) will be considered censored at their last documented study visit. If any measurement of laboratory data or ECG is available after the last visit of a patient, the date of the respective measurement will be used for censoring of the CV endpoint. If any measurement of eGFR is available after the last visit of a patient, the date of the respective measurement will be used for censoring of the renal endpoint. For all endpoints including the component CV (renal) death, adjudicated CV (renal) death will be counted even if occurred thereafter.

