If the event distribution is lower than expected, the impact on the study conduct should be carefully considered. The SC would further monitor the recruitment of the trial with regard to baseline data for CV complications and renal impairment. The intent is to obtain a balanced mix of patients with CV complications and albuminuria AND patients with renal impairment. As such the SC may recommend to cap specific patient populations.

If non-inferiority has been demonstrated, then superiority with regard to the primary endpoint will be tested. Assuming 625 **611** patients with event and a hazard rate on linagliptin at any time 20% less than the risk on placebo ( $HR: \lambda_{linagliptin}/\lambda_{placebo} = 0.02848/0.0356 = 0.80$ ), then the resulting power to demonstrate superiority at the final analysis is **74% 79%** if the **for a** test can be performed at the  $\alpha$ -level of **1.59% 2.5%** ([cf. Section 7.2](#)) and 69% if the test has to be performed at the  $\alpha$ -level of 1.06%. If the risk reduction is 21.3% (HR: 0.787) and the test can be performed at the  $\alpha$ -level of 1.59%, the power to demonstrate superiority is 80%; the power is 75% if the test has to be performed at the  $\alpha$ -level of 1.06%.

Assuming 432 patients with a composite renal endpoint, a yearly event rate of 2.5% in the placebo group and a hazard rate **HR** on linagliptin of 0.75, then the resulting power to demonstrate superiority at the final analysis is **80% 85%** if the test can be performed at the  $\alpha$ -level of 1.59% and 75% if the test has to be performed at the  $\alpha$ -level of 1.06% **2.5%**. **If the HR is 0.70, 210 patients with renal event provide a power of 73%.**

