#### 5.2 SECONDARY ENDPOINTS

#### 5.2.1 Key secondary endpoint

The key secondary endpoint is time to the first occurrence of any of the following by adjudication confirmed components: renal death, sustained end stage renal disease (ESRD) or sustained decrease of 40% or more in eGFR from baseline. This endpoint will also be further referred to as composite renal endpoint 1.

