## 6.8.3 Censoring

Primary endpoints

The underlying principle is that the censoring date should be the date at which the patient was last known to be free of an endpoint event (e.g. free of each component of the 3P-MACE).

Patients without occurrence of a specific endpoint (composite endpoint or individual components) will be considered censored at the individual day of trial completion\*.

- \* This is defined as the latest of the following dates as of
  - adverse event/outcome event start dates (if non-fatal event),
  - onset dates of adjudicated (by adjudication confirmed and non-confirmed) events (if non-fatal event),
  - date of trial completion (defined as latest of date of last clinic visit, last telephone contact, date of last contact if lost to follow-up).

For patients who died during the study, the date until which follow-up for non-fatal outcome events was performed will be used for censoring.

Censoring is considered independent from trial drug intake.

Generally, the 7 days censoring definition will be used for adverse events incl. hypoglycaemia.

All of the above mentioned x-day censoring rules will be handled as follows:

Patients who did not experience the event will be censored at the earliest date between the individual day of trial completion (defined above) and x days after last intake of study drug. For this analysis events will be considered that occurred not later than x days after last intake of study drug, or until individual day of trial completion (defined above), whichever is earlier.

Endpoints based only on laboratory data (by adjudication confirmed or not)

Patients who already fulfil the respective condition at baseline are generally not considered in the number of patients at risk for this endpoint (

If a baseline laboratory measurement is not available for the parameter of interest, it is assumed that the patient did not experience the condition corresponding to the endpoint at baseline and the patient is included in the patients at risk for this endpoint.

Patients without an event and available post-baseline laboratory measurements will be considered censored at the date of last laboratory sampling of the corresponding parameter. Patients with missing baseline laboratory required to derive a change from baseline and patients without laboratory data following the baseline measurement will be censored on the day of randomisation or date of first study drug intake, respectively.

Page 51 of 80

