## 7.5 SECONDARY ENDPOINTS

# 7.5.1 Key secondary endpoint

Main analysis of key secondary endpoint

The key secondary endpoint will be analyzed on the TS in the same way as described in Section 7.4.1 and Section 7.4.2 for the primary endpoint.

The hazard ratio (HR) for the effect of treatment (linagliptin vs. placebo), adjusted for geographical region, will be presented with the 95% confidence interval, the 96% confidence interval, and the p-values based on the Wald Chi-Square statistic: the one-sided p-value for the superiority test and the two-sided p-value.

The time to first occurrence will be counted from the date of randomisation. The censoring rules are described in Section 6.8.3.

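### Landmark Kaplan-Meier rates for the renal composite treat non-renal death as censoring, so they modestly overstate the cumulative incidence if read as absolute risk

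*SAP*

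**What the plan says.** SAP 7.4.2, written for the primary endpoint, plans Kaplan-Meier failure curves, failure-time quantiles and fixed-time rates: "Kaplan-Meier estimates for failure rates at 6 months, 1, 1.5, 2, etc years after randomisation will be presented per treatment group". SAP 7.5.1 carries this to the renal composite: "The key secondary endpoint will be analyzed on the TS in the same way as described in" Sections 7.4.1 and 7.4.2. It refers to SAP 6.8.3 for censoring.

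The renal composite (SAP 5.2.1) is "renal death, sustained end stage renal disease (ESRD) or sustained decrease of 40% or more in eGFR from baseline". Cardiovascular and other non-renal deaths are not events. Protocol 7.1 agrees: after a patient's last visit, "adjudicated CV (renal) death will be counted even if occurred thereafter", which for the renal endpoint means renal death only.

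SAP 6.8.3 sets the rule for patients without the endpoint: "Patients without occurrence of a specific endpoint (composite endpoint or individual components) will be considered censored at the individual day of trial completion". For deaths it adds: "For patients who died during the study, the date until which follow-up for non-fatal outcome events was performed will be used for censoring". That section has a separate rule for endpoints based only on laboratory data, which uses the last sampling date. Under either rule, a patient who dies of a non-renal cause without a renal event is censored.

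SAP 7.4.2 also plans the crude proportion with an event and the incidence rate per 1000 years at risk. The public text contains no cumulative incidence function for the renal endpoint.

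**The concern.** A patient who dies of a myocardial infarction can no longer reach end-stage renal disease or a 40% fall in eGFR. Censoring that patient makes Kaplan-Meier act as if the later renal risk were the same as that of the patients still alive. One minus Kaplan-Meier then estimates the renal risk that would apply if nobody died of anything else.

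The trial population makes this more than a formality. Patients enter with albuminuria plus macrovascular disease and/or impaired renal function, with eGFR down to 15 (Protocol 3.3.2). Protocol 1.1 attributes 70-75% of deaths in people with diabetes to cardiovascular complications. Exclusion criterion 11 limits short life expectancy only from non-cardiovascular causes.

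At stake is how the descriptive percentages will be used. The renal composite is the key secondary endpoint and carries 0.8 of the superiority alpha. Its yearly percentages by arm are likely to be quoted as absolute risks, and differences between them as absolute benefit. The excess grows with follow-up.

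**Working it through.** **The plan's own figures.** Protocol 7.6 uses F(t) = 1 - exp(-λt). With its λ of 0.0356 and t = 3.8 years, F = 1 - exp(-0.1353) = 12.65%, against 12.7% stated for the initially planned primary endpoint. The documents state no cumulative renal proportion. The renal power figures also reproduce, using power = Φ(½√D·|ln HR| - 1.96) with D the number of events:
- 432 events, HR 0.75: Φ(2.990 - 1.960) = 84.8% (stated 85%).
- 210 events, HR 0.70: Φ(2.584 - 1.960) = 73.4% (stated 73%).

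**Direction.** Let d be the renal events and Y the patients at risk at each event time.
- 1 minus Kaplan-Meier adds up S_KM(t-)·d/Y, where S_KM falls only at renal events.
- Aalen-Johansen adds up S_all(t-)·d/Y, where S_all falls at renal events and at non-renal deaths.

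S_all is never above S_KM, so 1 minus Kaplan-Meier is the larger whenever non-renal deaths precede later renal events. This needs no constant-hazard assumption.

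**Size: inputs.**
- Renal rate on placebo, from Protocol 7.6: "Assuming 432 patients with a composite renal endpoint, a yearly event rate of 2.5% in the placebo group". Hazard λr = -ln(0.975) = 0.02532.
- Non-renal death rate: not in the documents. Assumed 2% to 5% per year, so λd = -ln(0.98) = 0.02020 to -ln(0.95) = 0.05129.
- Constant, independent hazards (assumed).

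**Formulas.** 1 - KM = 1 - exp(-λr·t). Cumulative incidence = λr/(λr+λd) × [1 - exp(-(λr+λd)·t)].

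**Worked at 4 years.**
- 1 - KM = 1 - exp(-0.1013) = 9.63%.
- Death 2% per year: 0.5562 × [1 - exp(-0.1821)] = 0.5562 × 0.1665 = 9.26%. Excess 0.37 points, 4.0% relative.
- Death 5% per year: 0.3305 × [1 - exp(-0.3064)] = 0.3305 × 0.2639 = 8.72%. Excess 0.91 points, 10.4% relative.

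| Years | 1 - KM | Cumulative incidence (death 2% to 5%/yr) | Excess, points |
|---|---|---|---|
| 1 | 2.50% | 2.48% to 2.44% | 0.02 to 0.06 |
| 3 | 7.31% | 7.10% to 6.79% | 0.21 to 0.53 |
| 3.8 | 9.17% | 8.83% to 8.35% | 0.34 to 0.83 |
| 4 | 9.63% | 9.26% to 8.72% | 0.37 to 0.91 |

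Widening the assumed death rate to 1% to 6% per year gives an excess of 0.17 to 0.98 points at 3.8 years. A simulation of 400,000 patients at 3% per year gave 9.21% by Kaplan-Meier and 8.71% by Aalen-Johansen at 3.8 years. The formulas give 9.17% and 8.67%.

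**Sensitivity to the renal rate.** If it were 5% per year (assumed), the 3-year figures would be 14.26% against 13.85% to 13.25%, an excess of 0.41 to 1.02 points. The relative excess barely changes (3.0% to 7.7%, against 3.0% to 7.8%).

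**Risk difference.** With HR 0.75 and equal death rates of 2% to 5% per year in both arms, the 3.8-year difference is 9.17% - 6.96% = 2.21 points by Kaplan-Meier. By cumulative incidence it is 2.13 to 2.01 points.

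**The case against.** The strongest reply is that Kaplan-Meier is not an error here but a different estimand. The SAP calls these figures failure rates, not absolute risks, and the public text plans no absolute risk difference. Kaplan-Meier is also the display that goes with a Cox cause-specific hazard ratio and a log-rank test. This stands. The overstatement arises only when the figures are read as absolute risk, but nothing in the visible plan guards against that reading.

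Second, other measures are planned: crude proportions, rates per 1000 years, and Wilson intervals with a caution about survival and observation time (Protocol 7.3.2). None of them relies on censoring deaths in the Kaplan-Meier way. But none gives cumulative risk at a fixed time either.

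Third, SAP 7.4.3, 7.4.4 and 7.6.1 are cited in SAP Section 4 but are not in the public text. A competing-risk analysis may sit there. This stands as a limit. Such an analysis would supplement the Kaplan-Meier rates without changing what they estimate.

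Fourth, the effect is small, and few patients reach the later landmarks. With 36 months of recruitment in a 54-month trial and uniform accrual (assumed), (54 - 48)/36, or one-sixth, could be followed for 4 years. This also stands.

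A reader might go further and infer that Kaplan-Meier should be dropped, or that the 3P-MACE percentages are distorted to a similar degree. The documents do not support either. Protocol 7.3.1 requires Kaplan-Meier estimates by arm for the primary analysis. For 3P-MACE, cardiovascular death is itself an event, so only non-cardiovascular death competes. The effect there should be milder, and no figure in the documents lets it be sized.

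**Conclusion.** The point holds as a cheap improvement to descriptive reporting. The direction is certain once non-renal deaths occur. The size rests on an assumed 2% to 5% per year of non-renal death, the protocol's 2.5% renal rate, and constant independent hazards. On that basis the excess is about 0.2 to 0.5 points at 3 years and 0.4 to 0.9 points at 4 years (about 4% to 10% relative at 4 years), and negligible at 1 year.

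A reader might infer that the renal superiority test or its power is compromised. It is not. The Cox model and log-rank test compare cause-specific hazards, for which censoring other deaths is the usual handling. The alpha split does not depend on the landmark rates, and the power figures depend only on event counts and hazard ratios.

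Nor do the documents show that Kaplan-Meier would exaggerate the treatment benefit in general. The small excess in the risk difference was worked out for equal mortality in both arms. If mortality differs, the discrepancy can go either way.

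**What to change.** In SAP 7.5.1, add Aalen-Johansen cumulative incidence curves and rates for the renal composite, at the same time points and by arm, with non-renal death as the competing event. State that these estimates will be used for any statement of absolute renal risk or risk difference. Label any renal Kaplan-Meier rates that are kept as treating non-renal death as censoring. The added text should also say how a non-renal death is dated when renal follow-up ended before it, because SAP 6.8.3 currently uses the end of that follow-up.

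Keep the Cox hazard ratio as the confirmatory analysis, and keep the Kaplan-Meier display that Protocol 7.3.1 requires for 3P-MACE. If an unpublished SAP section already contains a competing-risk analysis, a cross-reference and the label are enough.

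The cost is one extra table and figure and a short SAP addition. The reported renal percentages will be slightly lower, and readers will see two sets of renal figures if Kaplan-Meier is kept, which is why the label matters.

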## 7.5 SECONDARY ENDPOINTS

# 7.5.1 Key secondary endpoint

Main analysis of key secondary endpoint

The key secondary endpoint will be analyzed on the TS in the same way as described in Section 7.4.1 and Section 7.4.2 for the primary endpoint.

The hazard ratio (HR) for the effect of treatment (linagliptin vs. placebo), adjusted for geographical region, will be presented with the 95% confidence interval, the 96% confidence interval, and the p-values based on the Wald Chi-Square statistic: the one-sided p-value for the superiority test and the two-sided p-value.

The time to first occurrence will be counted from the date of randomisation. The censoring rules are described in Section 6.8.3.

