I For female patients (local urine pregnancy test in women of child bearing potential). More frequent testing can be done if required by local regulations/authorities.

J Distribution of glucometer and testing supplies with instructions at randomization (visit 2). During the treatment period, weekly finger stick glucose measurements are recommended (fasted). During the whole trial participation, additional measurements should be done if necessary and in case of hypo- or hyperglycaemia related symptoms. The patient should be instructed to bring their HBGM device and diary to the clinic for an additional measurement (fasted).

Proprietary confidential information.

© 2016 Boehringer Ingelheim International GmbH or one or more of its affiliated companies. All rights reserved.

This document may not - in full or in part - be passed on, reproduced, published or otherwise used without prior written permission.

K At visit 1 safety laboratory includes ALT, AST, alkaline phosphatase and creatinine to check for eligibility in addition to lipase, urine albumin, urine creatinine and HbA1c as specified in the [flow chart](#). At randomization (visit 2) baseline laboratory will be obtained. [See section 5.2.3](#) for to be obtained laboratory parameters. As of visit 6: yearly (every other visit) lipid profile (Total cholesterol, HDL cholesterol, LDL cholesterol and triglycerides), urine albumin and urine creatinine.

L Estimated ~~creatinine~~ **glomerular filtration rate (eGFR)** will be calculated using the MDRD formula. This formula considers the race as an adjustment factor, therefore, the race must be known (and will be collected) for accurate estimation. In case of an eGFR decrease of  $\geq 40\%$  since baseline (visit 2) and again in case of an eGFR decrease of  $\geq 50\%$  since baseline (visit 2) an additional visit 4-8 weeks after detection should be scheduled to collect a blood sample for repeat analysis of creatinine (eGFR). An additional sample of creatinine should also be taken between the visits if a signal of increasing creatinine is reported to the study site by others (e.g., GPs from local labs).

M In case of a stroke the reported value from the modified Rankin Scale will be collected approximately one week after stroke onset and 3 months after stroke onset. This might require an additional contact.

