II.		
Evidence of impaired renal function with predefined UACR, with or without CV comorbidities, defined as follows (and/or criteria):
 

• Impaired renal function (as defined by MDRD formula) with an eGFR: <math>15- < 45</math> mL/min/<math>1.73\text{ m}^2</math> at visit 1 (screening) with any UACR.

• Impaired renal function (as defined by MDRD formula) with an eGFR <math>\geq 45-75</math> mL/min/<math>1.73\text{ m}^2</math> at visit 1 (screening) with an UACR <math>> 200</math> mg/g creatinine or <math>> 200</math> <math>\mu\text{g}/\text{min}</math> (microgram albumin per minute) or <math>> 200</math> mg/24 h [milligram albumin per 24 hours] demonstrated in two out of three unrelated spot urine or timed samples in the last 24 months prior to randomization*.

\*If the UACR result at Visit 2 is required to fulfil inclusion criterion 8, randomization may be postponed until the laboratory results are known.

Note: To ensure appropriate representation of patients from the different CV risk categories, the trial team will monitor the proportion of patients being recruited into these categories (trial level, and by region and/or country if appropriate). In consultation with the SC, limitation of recruitment of a particular category may be arranged (trial level, or per region and/or country level). This process will be implemented to ensure a proper distribution of CV risk categories worldwide.

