#### *Visit 2 (baseline):*

- Haematology: haematocrit, haemoglobin, erythrocyte count, platelet count and total and automates differential leukocyte counts (in absolute counts).
- Clinical chemistry: ALT, AST,  $\gamma$ -GT, AP, lipase, lactate dehydrogenase (LDH), total bilirubin, albumin, potassium, Sodium, creatinine, urea, calcium, inorganic phosphorous, urid acid, cholesterol (total), high density lipoprotein (HDL) cholesterol, low density lipoprotein (LDL) cholesterol and triglycerides.
- Urine analysis: albumin, creatinine, protein and leucocytes.

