### 7.3.1 Primary analyses

A classical ITT-approach on the FAS **TS** will be performed as described above. For the primary analysis a Cox proportional hazards regression model of time to the first event with randomized treatment and geographical region as factors will be applied. Kaplan-Meier estimates by treatment group will be displayed. The confirmatory test approach is outlined in [Section 7.2](#).

No centre effect will be included into the Cox models, as the centre size is expected to be small. Furthermore, due to the low event rate there would not be a sufficient number of events per centre for the analysis of a centre effect and a centre by treatment interaction.

For the primary and key secondary endpoints, sensitivity analyses will be done on the PPS, for the '~~30 days treatment~~' set **OS** and as ~~an 'on treatment'~~ a '**TS+30**' analysis as described below. These sensitivity analyses will be performed based on the corresponding patient sets for the time patients are on-treatment + 30 days after permanent treatment discontinuation or end of observation, whichever comes first. The '~~on treatment analysis~~' '**TS+30**' analysis will be performed on the FAS **TS** (consisting of all ~~randomized~~ patients who were treated with at least one dose of study drug) with censoring at the time patients are on treatment + 30 days after permanent treatment discontinuation or end of observation, whichever comes first.

For these sensitivity analyses, the randomized study treatment ('as randomized') will be used for treatment assignment.

To check the proportional hazards assumption, Schoenfeld residuals will be plotted for each covariate versus time; in addition,  $\ln(-\ln(S(t)))$  will be plotted vs. time and checked for

Proprietary confidential information.

© 2016 Boehringer Ingelheim International GmbH or one or more of its affiliated companies. All rights reserved.

This document may not - in full or in part - be passed on, reproduced, published or otherwise used without prior written permission.

parallelism. As a further assessment the interaction of covariates with time will be investigated. In case the proportionality assumption does not hold, a stratified log-rank test will be performed.

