## 6.7 BASELINE, TIME WINDOWS AND CALCULATED VISITS

#### 6.7.1 Baseline

The term "baseline" refers to the last available measurement prior to administration of any randomised trial medication.

The following considerations apply for laboratory measurements, if the time of the sample is missing on the day of first study medication intake:

- a) For FPG: the measurement will not be considered as baseline
- b) For all other lab investigations: The last measurement on this day will still be considered as baseline measurement.

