#### Statistical methods

For the primary analysis, a Cox proportional hazard regression model will be performed to compare the effect of linagliptin versus placebo. The model will include randomised treatment and geographical region as factors. Breslow's method will be used for dealing with ties. The SAS PHREG procedure will be used.

The hypothesis of non-inferiority will be tested at the one-sided significance level of  $\alpha_1$ =2.5%.

The hazard function of an event for patient j at time t is assumed to have the form:

$$h_i(t) = \exp(\beta_1 x 1_i + \beta_2 x 2_i) h_0(t), j=1,...,n,$$

where

- $\circ$  h0(t) is the non-negative baseline hazard function for a patient with a value of zero for the explanatory value  $x1_i$  and  $x2_i$
- o β1 is the (unknown) coefficient of the explanatory variable x1
- $\circ$  x1j is an indicator variable representing the treatment group for patient j=1,...,n

- o β2 is the (unknown) coefficient of the explanatory variable x2
- o x2j is an indicator variable representing the geographical region for patient j=1,...,n

The hazard ratio (HR) for the effect of treatment (linagliptin vs. placebo), adjusted for geographical region, will be presented with the 95% confidence interval, the 99% confidence interval and the p-values based on the Wald Chi-Square statistic: one-sided p-value for the non-inferiority test (NI margin 1.3), the one-sided p-value for the superiority test and the two-sided p-value.

Non-inferiority of the primary endpoint will be investigated by comparing the upper limit of the two sided 95% confidence interval of the hazard ratio with the non-inferiority margin of 1.3: if the upper limit is less than 1.3, non-inferiority has been demonstrated.

In case non-inferiority of the primary endpoint is demonstrated, then superiority of the primary endpoint and superiority of the key secondary endpoint will be investigated:

For the final analysis, the first hypothesis (non-inferiority of the primary endpoint) will be tested at the one-sided alpha-level of 2.5%. In case of significance, the null hypothesis is rejected in a confirmatory sense and the next set of hypotheses (two separate hypothesis tests) will be tested: a) test of the primary endpoint for superiority and b) test of the composite renal endpoint for superiority.

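### The confirmatory renal superiority test is valid but adjusts for region only; pre-specifying baseline eGFR and UACR as covariates would add some power without new data

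*SAP*

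**What the plan says.** SAP 7.5.1 sets the main analysis of composite renal endpoint 1 (renal death, sustained ESRD, or a sustained eGFR fall of at least 40%) by reference: "The key secondary endpoint will be analyzed on the TS in the same way as described in" SAP 7.4.1 and 7.4.2. For the Cox model there, SAP 7.4.1 states: "The model will include randomised treatment and geographical region as factors". SAP 7.5.1 then reports a region-adjusted hazard ratio with 95% and 96% intervals and a Wald p-value. The protocol synopsis and protocol 7.3.1 describe the same model. Region is also the only stratification factor (protocol 7.5).

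Both baseline renal measures are collected in any case. The flow chart schedules eGFR and UACR at screening and at visit 2. Its footnote K says: "At randomization (visit 2) baseline laboratory will be obtained". Protocol 5.2.3 lists for visit 2: "Urine analysis: albumin, creatinine, protein and leucocytes". SAP 6.7.1 already defines baseline: the term "refers to the last available measurement prior to administration of any randomised trial medication".

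In the readable text, baseline renal status enters the analysis of this endpoint only through the exploratory subgroups of protocol 7.3. SAP 7.4.3, 7.4.4 and 7.6.1 are not in the public text and may contain an adjusted sensitivity analysis. That would not alter the confirmatory model.

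**The concern.** Inclusion criterion 8 admits patients of very different renal risk: eGFR from 15 to below 45 with any UACR, eGFR 45 to 75 with UACR above 200 mg/g, or albuminuria with macrovascular disease and no upper eGFR limit. If baseline eGFR and UACR predict the renal outcome, leaving them out of the Cox model pulls the estimated hazard ratio towards 1 and costs power. It does not inflate the type I error.

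The renal test carries much of the superiority strategy. Under protocol 7.2 and SAP 7.4.1 it starts with 0.8 × 2.5% = 2.0% one-sided, and its success raises the MACE superiority test from 0.2 × 2.5% = 0.5% to the full 2.5%. With 611 events and HR 0.80, the power for MACE superiority is about 57% at 0.5% and 79% at 2.5%. A missed renal rejection can therefore cost both claims.

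**Working it through.** **Inputs.** From protocol 7.6: 432 renal events with HR 0.75 (stated power 85%); 210 renal events with HR 0.70 (stated power 73%); 611 MACE events with HR 0.80 (stated power 79%); about 7000 patients, 1:1. From protocol 3.1: 36 months of recruitment and 54 months in total, hence 1.5 to 4.5 years of follow-up. From protocol 7.2: the alpha split. The prognostic strength of eGFR and UACR is not in the documents and is assumed.

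**Step 1: reproduce the stated power.** Schoenfeld: power = Φ(√(D/4) × |ln HR| − z).

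- 432 events, HR 0.75: √108 × 0.2877 = 2.990. At 2.5% (z = 1.960), Φ(1.030) = 84.8%, against 85% stated.
- 210 events, HR 0.70: √52.5 × 0.3567 = 2.584. At 2.5%, Φ(0.624) = 73.4%, against 73% stated.

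**Step 2: power at the level where the renal test starts.** At one-sided 2.0% (z = 2.054):

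- 432 events: Φ(0.936) = 82.5%.
- 210 events: Φ(0.531) = 70.2%.

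**Step 3: effect of adjustment, by simulation.** 3000 trials per scenario; n = 7000; exponential event times; follow-up uniform from 1.5 to 4.5 years; two independent normal covariates with the combined log-hazard SD shown; no region term in either model. The conditional HR was set so that the unadjusted HR equals the planned 0.75 or 0.70. Powers are rejection rates at one-sided 2.0%.

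| Log-hazard SD | 432 events: unadjusted → adjusted | Gain (points) | 210 events: unadjusted → adjusted | Gain (points) |
|---|---|---|---|---|
| 0.5 | 81.8% → 82.9% | 1.1 | 68.9% → 69.1% | 0.2 |
| 0.8 | 81.8% → 84.7% | 2.9 | 69.2% → 70.0% | 0.8 |
| 1.2 | 81.8% → 87.3% | 5.5 | 67.3% → 72.2% | 4.9 |
| 1.5 | 81.5% → 90.1% | 8.6 | 68.9% → 75.3% | 6.4 |

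The Monte Carlo standard error of each gain is 0.3 to 0.6 points. The squared ratio of mean z-values gives the equivalent increase in events: 1.02, 1.06, 1.18 and 1.30 with 432 events (2% to 30% more), and 1.01, 1.03, 1.09 and 1.17 with 210 (1% to 17% more).

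**Step 4: a second simulation built differently.** It used four regions in both models, correlated covariates (0.3) and 400 trials per scenario, and applied the ratio of mean z-values to the Schoenfeld calculation. Its moderate and strong cases (HR per SD of eGFR / log UACR of 1.5/1.8 and 1.8/2.5) correspond to log-hazard SDs of about 0.8 and 1.2. With 432 events at 2.0% they give 84.7% and 88.4%, close to step 3. In the strong case the standard error hardly moves (0.0968 unadjusted, 0.0969 adjusted), while the HR moves from 0.768 to 0.750. The gain comes from less attenuation.

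**Step 5: validity.** Under the null with strong covariates (3000 trials), the region-only model rejected in 2.53% and the adjusted model in 2.73% of trials at nominal 2.5%, with a Monte Carlo standard error of 0.29 points. Both are consistent with the nominal level.

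**Step 6: missing baseline values.** With 5% of each covariate missing and filled with the mean (2000 trials, 432 events, SD 1.2), power still rose from 83.0% to 87.2%.

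**The case against.** The strongest reply is that nothing is wrong: the stratification factor is in the model, the stated power reproduces under that model, and the benefit rests on a prognostic strength the documents do not give. At SD 0.5 to 0.8 the gain is only 1.1 to 2.9 points (432 events) or 0.2 to 0.8 (210 events), the smallest being within simulation error. SD 1.5 implies roughly a 20-fold hazard difference (e³) between patients one SD above and one SD below the mean. This stands, and is why the point is a suggestion with a range.

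The simulation also assumes the right covariate form. Baseline eGFR helps define the endpoint: a patient starting at 20 passes the ESRD threshold of 15 after a 25% fall, while a patient starting at 70 meets the 40% criterion first, so log-linearity is doubtful. The gains in step 3 are therefore best-case. A further check with a deliberately non-log-linear covariate effect still gave a squared z-ratio of 1.18, and the null rejection rate was not inflated (1.4% against 2.0%).

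The 82.5% and 70.2% ignore alpha passed back from MACE. If MACE superiority has HR 0.80 and the two tests are independent (both assumptions), renal power becomes 82.5% + 0.57 × (84.8% − 82.5%), about 83.9%, and likewise about 72.0%. This shifts the starting point slightly and does not remove the gain.

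Finally, the SAP had already been revised on FDA advice and the revisions accepted in November 2017 (SAP section 4), and the adjusted HR is a different effect measure. Both are real costs.

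**Conclusion.** The point holds as a recommended improvement to a valid test. The confirmatory renal model ignores two baseline measures that the trial collects from everyone. Adjusting for them is worth about 1 to 9 power points with 432 events and about 0 to 6 with 210, at the initial one-sided 2.0% level. The range depends on an assumed combined log-hazard SD of 0.5 to 1.5, a correctly specified covariate form, and the planned HRs being read as effects in the planned model. If the covariates are only weakly prognostic the gain is negligible. Confidence is medium because the prognostic strength cannot be taken from the documents.

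**What to change.** Before unblinding, amend SAP 7.5.1 as follows.

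1. Add continuous baseline eGFR and log-transformed baseline UACR to the confirmatory Cox model for composite renal endpoint 1, using the SAP 6.7.1 baseline definition.
2. For patients without a baseline value, fill in the overall baseline mean or median, pooled over both arms, so that they stay in the Treated Set analysis. SAP 6.8.3 has a rule beginning "If a baseline laboratory measurement is not available for the parameter of interest", but it concerns the at-risk set for laboratory endpoints, not covariates.
3. Judge the proportional-hazards fallback on the treatment term alone. Protocol 7.3.1 says: "To check the proportional hazards assumption, Schoenfeld residuals will be plotted for each covariate versus time", and it switches to a stratified log-rank test if proportionality fails. Without this limit, either new covariate could trigger the switch and lose the gain.
4. Keep the region-only model as a sensitivity analysis and leave the MACE model unchanged.

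No new patients, events or measurements are needed. The change must be listed in SAP section 4, or the protocol text aligned (the model is stated in the synopsis and 7.3.1, the key secondary analysis in 7.3.2). The SAP must also say which hazard ratio is reported. The adjusted one is conditional on baseline renal status (for example 0.734 against 0.75 at SD 1.2 with 432 events): a different quantity, not a bias correction.
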